2.5.3 Protection Against Risks

As indicated above, we expect minimum risk to participants. The primary pre-defined serious adverse events related to this study includes hypoglycemia among patients with diabetes mellitus starting a new exercise program. Subjects with any form of diabetes will be instructed to talk with their diabetes care team about adjusting their diabetes medication before starting a new exercise regimen and to discuss ways to treat hypoglycemia. Additionally, these recommendations will be reinforced with a handout from our study team about risk of hypoglycemia, signs, symptoms, and treatment of hypoglycemia and how to decrease their risk of hypoglycemia.

Patients with advanced chronic kidney disease (on dialysis or seeing a nephrologist) will be excluded to avoid serious adverse events with the Dietary Approaches to Stop Hypertension (DASH) diet, which may cause hyperkalemia. Once enrolled, study protocols will monitor and assess the presence of adverse events (AEs) and serious adverse events (SAEs) at all follow-up contacts.

Should a serious adverse event or adverse event be identified, it will be immediately reported as outlined later in this protocol. Should excessive risk to study participants be determined, the study will be stopped and all participants notified in a manner appropriate to the nature of the risk.

Emails will be used for sending 1) research clinic visit appointment reminders for all subjects (day, time, location, directions to UWHC or UWSMPH) and 2) handouts on blood pressure topics to reinforce the health coach phone call (intervention arm only - if this method was selected by the subject over postal mail). Each email will contain the minimum amount of information needed. Emails will be sent individually, with no cc or bcc. No group emails or lists will be used for this study. Emails will not contain sensitive protected health information (PHI). Per the University of Wisconsin HIPAA policy (www.hipaa.wisc.edu), the subject of the email will be "Documents for your UW Study".

Blood Pressure Cuffs: To minimize risks, patients will receive the appropriately sized cuff based on their upper arm circumference. In addition, the 24-hour ambulatory monitor will be started prior to leaving the research clinic to obtain at least two blood pressures to ensure comfort. Participants will also review information on how to contact the research staff in case additional questions, concerns, or new discomfort arise.

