3.1.3 Primary Safety Endpoints

- Number and type of adverse events
- Number and type of serious adverse events
- Subject Withdrawal rate and reason

4 Study Subjects – Enrollment and Withdrawal

See Appendix for accrual expectations by research site

The recruitment and screening protocol will be the same at both sites. The accrual goal is 340 participants total (n=170 per arm) over 25 months of recruitment. Participants will be randomized to control or intervention arms at each site.

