5.3 Established Standard of Care

Usual care and intervention arm participants will receive routine hypertension clinical care per their primary care provider. This includes the possibility of receiving untailored self-management resources (i.e., dietitian referral) at their provider's discretion, but this is not systematically tailored to young adults' needs. These patients would be treated according to current hypertension guideline standards including, but not limited to, hypertension lifestyle modification counseling: 1) reduced sodium intake, 2) weight loss, 3) reduced alcohol consumption, and 4) increased physical activity. This may include verbal discussions and/or handouts. Medications would be initiated and/or titrated per hypertension guidelines.

All patients would have clinic blood pressure checks and would be encouraged to have home blood pressure monitoring. Additionally, providers may order 24-hour Ambulatory Blood Pressure Monitoring, per the U.S. Preventive Services Task Force guidelines, to exclude white coat hypertension. Patients would also have additional tests not limited to blood draws, EKGs, echocardiograms, etc.

We will assess the number of healthcare team contacts in the usual care arm by calculating the number of primary care and specialty visits and dietitian and exercise referrals after study enrollment (see IRB application with data variable sheet).^{50,60} Usual care arm participants will receive AHA's "What is High Blood Pressure"¹³¹ handout (copies of handouts are in the Appendix).¹³² It is usual care for patients to receive hypertension educational material when presenting for a hypertension visit. They will not receive home blood pressure monitors. Usual care participants will have the same 6- and 12-month assessments as the intervention arm.

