Health Coach Phone Calls: Intervention arm participants will receive a health coach phone call every 2 weeks for 6 months, for a total of 12 calls. The first call will be scheduled at the screening visit and subsequent calls will be set up at the end of each prior call. If a participant is unavailable, the health coach will leave a message and reschedule the call up to 3 times. Once a coach is ready to make calls for the MyHEART intervention: during each call, the health

coaches will review and discuss home blood pressures, if available, from home blood pressure monitoring, and address barriers and concerns to home blood pressure monitoring. The MyHEART coaches will also recommend clinic follow-up based on the 2-week average home blood pressures – see coach's guide, which coincides with UW Health's blood pressure follow-up recommendation. During each telephone call, the coach will guide the subject on selecting health behavior goals and completing the goal sheet (uploaded in this application). In addition to home blood pressure monitoring, subjects will be able to choose which topics from the 8 additional hypertension education modules they want to address during a call (options include: hypertension knowledge, low sodium, DASH eating plan, weight loss/maintenance, smoking cessation, moderate alcohol consumption, blood pressure medicine, social support and stress management). The coach may also offer topics to the participant based upon barriers or concerns discussed during the call. A module is a "topic" to discuss which includes a coach's education/counseling, associated handouts, and references (see module overview in table below). The participant may focus on the same topics throughout the intervention based upon their personal needs or change the topics with every call. Home blood pressure monitoring will be discussed during each call by the health coach.

MyHEART Health Coach Educational Modules	
Module	Topics
Home Blood Pressure Monitoring	How to measure blood pressure, include members in household to avoid isolation, what do the numbers mean
Hypertension Knowledge	Define blood pressure, goal blood pressure, long-term health consequences
Low Sodium	Reading labels, effects of sodium on blood pressure, culturally appropriate cooking alternatives, eating with peers, meal planning, shopping on a budget

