There is no interim analysis planned. However, we are prepared, if requested by the Data Safety and Monitoring Committee at any point, to calculate interim statistical power for its review. Projections of interim power can be made under several scenarios for future data, including assumptions that current trends continue or that the future data reflect the relative effects used in the design of the trial. Safety reports will tally adverse events by intervention assignment and postulated relationship to the trial interventions; event rates will be reported per person year of follow-up. Should excessive risk to study participants be determined during the data safety monitoring review, the study will

be stopped and all participants notified in a manner appropriate to the nature of the risk as defined by the IRB and DSMB.

7 Data Collection, Handling, and Record Keeping

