7.2 Data Capture

7.2.1 Source Documents

All source data will be kept and merged and/or entered into the electronic clinical trial software (REDCap). Source data is all information, original records of clinical findings, observations, or other activities in a clinical trial necessary for the reconstruction and evaluation of the trial. Source data are contained in source documents. Examples of these original documents and data records include: hospital records, clinical and office charts, laboratory notes, memoranda, subjects' diaries or evaluation checklists, recorded data from automated instruments, copies or transcriptions certified after verification as being accurate and complete, subject files, and records kept at the pharmacy, at the laboratories, and at medico-technical departments involved in the clinical trial.

Data will be collected at both study sites during the Screening Visit (Visit 1), Screening/Baseline assessment (Visit 2), 6-month Visits (Visits 3 and 4), 12-month Visits (Visits 5 and 6), and during the health coach phone calls.

In addition, 24-ambulatory blood pressure monitoring will be performed at each site with data downloaded via Spacelabs software and summary data transferred to REDCap. Data from these visits including participant

demographic information, vital signs, and other participant information will be uploaded into REDCap clinical research management software.

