8.3 Time Period and Frequency for Event Assessment and Follow-Up

The occurrence of an AE or SAE may come to the attention of study personnel during study visits and interviews of a study participant presenting for medical care, or upon review by a study monitor. All AEs including local and systemic reactions not meeting the criteria for SAEs will be captured on the appropriate CRF. Information to be collected includes event description, time of onset, clinician’s assessment of severity, relationship to study product (assessed only by those with the training and authority to make a diagnosis), and time of resolution/stabilization of the event. All

AEs occurring while on study must be documented appropriately regardless of relationship. All AEs will be followed to adequate resolution.

Any medical condition that is present at the time that the participant is screened will be considered as baseline and not reported as an AE. However, if the study participant's condition deteriorates at any time during the study, it will be recorded as an AE. UPs will be recorded in the data collection system throughout the study.

Changes in the severity of an AE will be documented to allow an assessment of the duration of the event at each level of severity to be performed. AEs characterized as intermittent require documentation of onset and duration of each episode.

The PI will record all reportable events with start dates occurring any time after informed consent is obtained until 30 days (for non-serious AEs and SAEs) after the last day of study participation. At each study visit, the investigator will inquire about the occurrence of AE/SAEs since the last visit. Events will be followed for outcome information until resolution or stabilization. Breaches of confidentiality and emotional upset will be reported to the PI who will then review the incident with the study staff, information technology groups, and follow-up with the participant. The PI is responsible for making the reports to the DSBM, IRB and NHLBI.

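### The by-arm adverse event comparison is at risk of unequal ascertainment, because only the intervention arm has 12 coach calls and the protocol does not settle whether those calls elicit events

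*Combined protocol and SAP*

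**What the plan says.** The first of the primary safety endpoints in Section 3.1.3 is "Number and type of adverse events". The safety reporting text in Section 6.3 states: "Safety reports will tally adverse events by intervention assignment and postulated relationship to the trial interventions". It adds that rates are per person-year of follow-up.

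Two passages describe when events are sought, and they differ:

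- Section 2.5.3: "study protocols will monitor and assess the presence of adverse events (AEs) and serious adverse events (SAEs) at all follow-up contacts".
- Section 8.3: "At each study visit, the investigator will inquire about the occurrence of AE/SAEs since the last visit". The same section also requires every event on study to be documented, whatever its relationship to the study.

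The contact schedules also differ. Section 5.4.2: "Intervention arm participants will receive a health coach phone call every 2 weeks for 6 months, for a total of 12 calls". Section 7.2.1 lists the occasions of data collection, ending with "12-month Visits (Visits 5 and 6), and during the health coach phone calls", but does not say whether event data are among them. For the control arm, Section 5.3 states: "Usual care participants will have the same 6- and 12-month assessments as the intervention arm". Section 5.4.5 adds one telephone follow-up in the 30 days after the 12-month visit, for both arms.

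Section 2.5.4 withdraws a subject immediately after any adverse or serious adverse event.

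**The concern.** Person-years adjust for time at risk. They do not adjust for the number of chances to report. If a coach asks about events every two weeks, or simply records what a participant volunteers, minor events in the intervention arm are caught close to onset. A usual-care participant is first asked at Visit 3 and must recall about six months.

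The events here are open to this. Section 8.1.1 defines an adverse event broadly, down to any symptom or experience, and Section 2.5.1 expects muscle or joint discomfort from new exercise. Coaches also review home blood pressures, in one arm only. Hospitalisations and deaths should be much less affected.

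The monitoring committee receives the number and seriousness of events (Section 8.6), and Section 6.3 links stopping the study to that safety review. Because Section 2.5.4 ties withdrawal to any event, unequal detection would also affect the withdrawal rate, another primary safety endpoint in Section 3.1.3. The text supplied contains neither a field for the source of a report nor a comparison restricted to contacts that both arms share.

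**Working it through.** **1. The plan's own figure.** One call every 2 weeks over 24 weeks gives 24/2 = 12 calls, as stated (26 weeks would give 13).

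**2. Named contacts after randomisation.** Scheduler calls (Section 5.4.3) and phone surveys (Section 9.4) are left out because their event content is not stated.

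| Period | Intervention | Usual care |
|---|---|---|
| Through Visit 4 | 12 calls + 2 visits = 14 | 2 visits = 2 |
| Whole study | 12 calls + 4 visits + 1 post-study call = 17 | 4 visits + 1 post-study call = 5 |

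All the excess falls in months 0-6. Twelve is the planned number of calls, not the number completed.

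**3. Apparent rate ratio with equal true rates.** Let r be the probability that an event is recalled at a visit, and c the probability that it is captured on a call. An event missed on the calls can still be recalled at the visit. Both r and c are assumptions; the documents give neither. With calls in the first half-year only and no withdrawal:

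- Months 0-6: ratio = [c + (1 - c)r] / r
- Months 0-12: ratio = {[c + (1 - c)r] + r} / (2r)

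Example: c = 0.5, r = 0.8 gives [0.5 + 0.5 × 0.8 + 0.8] / 1.6 = 1.7/1.6 = 1.06.

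| Visit recall r | c = 0, 0-12 | c = 0.5, 0-12 | c = 1, 0-12 | c = 1, 0-6 only |
|---|---|---|---|---|
| 1.0 | 1.00 | 1.00 | 1.00 | 1.00 |
| 0.8 | 1.00 | 1.06 | 1.13 | 1.25 |
| 0.6 | 1.00 | 1.17 | 1.33 | 1.67 |
| 0.5 | 1.00 | 1.25 | 1.50 | 2.00 |

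**4. Adding the withdrawal rule of Section 2.5.4.** I simulated 400,000 participants per arm with c = 1 and assumed true rates of 0.5, 1 and 2 events per person-year. An event caught on a call ends follow-up at that call. An event recalled at the 6-month visit ends it there.

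| Visit recall r | Person-year rate ratio | Raw tally ratio |
|---|---|---|
| 1.0 | 0.97-1.00 | 0.73-0.94 |
| 0.8 | 1.12-1.13 | 0.80-1.03 |
| 0.6 | 1.35-1.38 | 0.92-1.21 |
| 0.5 | 1.53-1.59 | 1.01-1.36 |

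The tally can fall below 1 because a participant withdrawn at a call stops contributing events, while a usual-care participant can accumulate several before Visit 3.

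**5. Common contacts only.** If only events elicited at Visits 3-6 and the 30-day call are compared, the expected ratio under equal true rates is r/r = 1.00 for any r. This requires the same recall in both arms and no loss of events through earlier withdrawal.

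**The case against.** The strongest reply is that Section 8.3, which governs the timing of event assessment, puts the inquiry at study visits and looks back to the previous one. Both arms share those visits. The call content in Section 5.4.2 covers home readings, barriers, goals and education modules, and lists no event question. The call logs and the full SAP are appendices outside the text supplied, and Section 2.5.4 promises standardised assessment of events. This stands as far as it goes: the documents do not show that the calls elicit events. It does not close the matter, because Section 2.5.3 read literally covers the calls, and Section 8.3 itself requires any event on study to be documented, so one volunteered to a coach would count.

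A reader might infer that the rates are biased against the intervention, by a 12-month ratio of 1.5 to 1.6 if capture were, say, 80% versus 50% or 90% versus 60%. The documents do not support that:

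- **Size.** The calls stop at month 6. An average capture of 80% over 12 months, with 50% in months 6-12, would need 2 × 0.8 - 0.5 = 110% in months 0-6; the second pair would need 2 × 0.9 - 0.6 = 120%. Applied to months 0-6 only, the pairs give (0.8 + 0.5)/1.0 = 1.30 and (0.9 + 0.6)/1.2 = 1.25.
- **Direction.** Under the withdrawal rule the raw tally can favour either arm, so it does not follow that the committee would see more events under MyHEART.
- **Consequence.** No test or numerical threshold for adverse events is given, reports are also split by postulated relationship, and an independent committee that includes biostatisticians reviews them.

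**Conclusion.** The concern holds as a risk, mainly for non-serious events in months 0-6. Sections 2.5.3 and 8.3 disagree on whether the coach calls are points of event assessment. If they are, and visit recall is incomplete, the person-year comparison is inflated in the intervention arm and nothing in the available text corrects it.

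The size depends wholly on assumed recall and call capture. Ignoring withdrawal, the 12-month ratio is 1.00 with complete recall or calls that elicit nothing. For visit recall of 0.8 to 0.5, it is about 1.06-1.25 at half capture and 1.13-1.50 at full capture. With withdrawal and full capture, the upper end reaches 1.59 at recall of 0.5, while the raw tally ratio over all cases simulated runs from 0.73 to 1.36. The point is modest, but it concerns a stated primary safety endpoint and is cheap to settle.

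**What to change.** 1. Reconcile Sections 2.5.3 and 8.3, stating whether coach calls elicit adverse events.
2. Add a source-of-report field in REDCap (common visit, 30-day call, coach call, other).
3. Ask the same structured question in both arms at the common visits and the 30-day call. It should cover the whole interval since the previous common visit, regardless of any coach call. A look-back only to the last time the participant was asked would shorten the intervention arm's window and could reverse the bias.
4. Base the between-arm comparison on those common-contact reports. List events reported only on coach calls separately, and show the rate with and without them.
5. Reconcile the withdrawal text in Section 2.5.4 with this comparison. State how an event followed by withdrawal before a common visit is counted, so that such events are not lost from the intervention arm.
6. Leave expedited reporting of serious events unchanged.

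The cost is one data field, one extra listing, and a main comparison that omits some minor call-only events, which are still reported.

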7.1 Data Confidentiality

Protecting Participant Confidentiality: Every effort will be made to protect participant confidentiality. Subject confidentiality will be protected with the coded patient IDs whenever possible. Linking information will be maintained separately from other study documents in a password-protected database on password-protected media. Only the principal investigator, HIP programmers, and the research coordinators responsible for mailing the study invitations and remuneration will have access to directly identifiable subject data. Once these activities have ceased, identifying information will be destroyed. Analysis datasets will be limited datasets and the research team will not have access to identifiers other than those in a limited dataset (zip codes and dates), or any cross-walk information.

Identifiable Data: HIP and Aurora Health Care Programmers will identify potential participants using the criteria described in this protocol. Each subject will be assigned a study-specific ID number, maintained separately from the subject's medical record number (MRN). Only research team members listed in the IRB application shall have access to the list.

Security levels for the UW Ob/Gyn and Health Innovation Program's data systems that include patient-identifiable data are housed within a UW Health data center (and benefit from the same security configuration as other UW Health servers housing fully identifiable clinical and administrative patient data) and include:

1. All new user account requests and access to any resource is reviewed and approved by the Health Innovation Program Director or UW Ob/Gyn IT director.
2. Resource administration is managed by the UW Ob/Gyn or Health Innovation Program's (HIP's) Compliance Officer and Information Technology personnel. UW Health user account creation is requested by HIP's Compliance Officer and fulfilled by UW Health Information Technology personnel.
 - a. A combination of Active Directory (AD) and New Technology File System (NTFS) folder permissions enforce authentication and file access policies.
 - b. Folder access permissions are routinely reviewed and compared to the project's list of "Key Personnel" and/or those persons specified elsewhere to have privileges to view/use the data (e.g., data use agreement or confidentiality agreement signatories).
3. These data systems are located behind UW Health's firewall.
4. These data systems are accessed via remote desktop connections originating from a subnet of Internet Protocol (IP) addresses reserved only for UW Ob/Gyn or Health Innovation Program computer workstations.
5. These HIP data systems at UW Health are secured in a data center behind a series of two locked doors; access is restricted to key UW Health Information Technology personnel under the supervision of the UW Health server administrator.

PC workstations used to access the server with identifiable data must be within HIP's subnet, which is preapproved by UW Health to access this server and have an additional layer of password protection.

The Aurora Health Care Research Analytics team and the Aurora Health Care Information Technology personnel oversee the security, user access, and data systems that include patient-identifiable data and transfer of encrypted, limited data sets to the UW Ob/Gyn or Health Innovation Program. The research analytics team has received extensive training and numerous certifications on obtaining data from Aurora's electronic health record. Each member of the research analytics team may serve as honest brokers and are skilled in de-identifying protected health information.

For Aurora Health Care:

1. Aurora Health Care Research Analytics, Aurora IRB/Compliance, and Aurora Information Technology teams review all new user account requests and access to any resource.

2. Aurora Health Care's database servers are secured via firewall, hardened to remove nonessential access credentials, and strong password compliance. Hosted systems are constantly monitored for latencies and intrusion.
3. There are differentiated user roles and privileges, password and user authentication security, electronic signatures, SSL encryption, and a comprehensive auditing record and monitoring of access and data changes to support the security of data transfer from Aurora Health Care to the Health Innovation Program.

At the Aurora site, paper source documents will be kept in a clinical research office at Aurora Health Care (Milwaukee, WI) which is double locked and only accessible by key card and/or key. After REDCap entry, source documents will be stored in subject binders in a locked filing cabinet and maintained for the length of time approved by the IRB.

Analysis Datasets: All research and analysis from the combined research sites will be conducted using a limited dataset (no direct identifiers; includes zip codes and dates only), provided by the Health Innovation Program.

Each individual patient record in the dataset is assigned a "pseudo ID" during dataset construction, which allows HIP and Aurora Health Care Programmers to link patient records from multiple sources and/or across different file types (e.g., demographics, laboratory results, medications). The pseudo ID also allows Programmers to cross-walk the data back to the Electronic Health Record ("EHR"; example: UW Health Link) in the event data need to be verified or additional elements extracted from the source. Information allowing data to be cross-walked with identifiers will never be shared with the study team.

Following data aggregation, linking, and variable creation, the datasets used for day-to-day analysis will be securely transferred to a second server with equivalent security. Data access is restricted to only IRB-approved personnel conducting study analysis and with passwords for computer drive and project folder access. The limited datasets are stored on a specified HIP server, housed in the Centennial Office Building managed by the UW SMPH IT, and is connected via fiber optic cable to the HIP suite at [name]. As of May 2022, all data will be transferred from HIP and stored on the UW Department of Obstetrics and Gynecology server. No individual PHI will be released for analysis, in presentation or publication. Only aggregate statistical output representing groups of subjects will be released. The completed study data set will be securely transferred, using the latest Secure File Transfer Protocol, to the Bioinformatics Computing Group (BCG) at the UW-Madison to the lead statistician. The levels of security for the server are five-fold and include:

- 1) Physical Security: server is located in an enterprise level secure data center under control of UW School of Medicine and Public Health (SMPH) ITS, which is a dedicated computer machine room requiring keycard and PIN for access. The room is equipped with camera surveillance, a hot and cold aisle chilling system and an automatic fire detection and suppression system. SMPH ITS does not have access to the server. Ob-Gyn servers are supplied power by redundant sources and are protected by both an uninterruptible power supply and a backup generator.
- 2) The data resides behind an SMPH managed hardware based firewall and a computer based software firewall
- 3) Access controls: Data directory access is limited to project PI and designees she approves (currently none at this time)
- 4) Domain access restrictions: access to Ob-Gyn computing resources is restricted to individuals with an Ob-Gyn logon
- 5) Authentication: Password protection is used at the network level for all transactions that allow entry and editing of data, provide access to EPHI data, or administrative activities.

Online Collaboration Tool: The Health Innovation Program developed a secure SharePoint-based Intranet. This web-based platform will be available to IRB-approved MyHEART investigators and staff to securely access this study's materials (examples: up-to-date protocols, contact information, calendars). Access to the UW Ob/Gyn or HIP Intranet follows the same secure measures as defined above.

Online Reporting Tool: This proposal will use the REDCap data management program. The REDCap application and data are hosted by the Bioinformatics Computing Group (BCG) at the UW-Madison on its server farm with redundant systems. To gain access to the REDCap system, study personnel will need to fill out a REDCap account request through ICTR using the following link: <https://redcap.ictr.wisc.edu/surveys/?s=MPHF4FWP4D>.

Once approved, each user will have their own account. To ensure that REDCap users have access only to data and information that they are supposed to have access to within the application, the each user's privileges will be assigned by the study's principal investigator. The *Data Access Groups* functionality will also be implemented to allow site-specific research staff to only access records created at their respective site.

Additional REDCap security features that will be used in this study include:

- authentication to validate the identity of end-users that log into the system
- auto-logout setting
- Limit number of failed login attempts before a user is locked out of the system

REDCap data entry, views, and modification will be audited for each user. A user's status will be immediately suspended if an audit demonstrates that they are not complying with the protocol and the IRB and DSMB will be notified per the IRB policy.

Disaster recovery plans include a back-up server at the UW Centennial Medical Building, independently managed by the UW School of Medicine and Public Health, Department of Medicine.

We also have policies and procedures in place to protect the confidentiality and security of patient data, and our data protection measures (for protected health information, or PHI) are consistent with the Federal Health Insurance Portability and Protection Act's privacy and security rules (45 CFR §160.103; 45 CFR §160 and 164, Subparts A and C, respectively). Only persons directly involved in the research will have access to identifiable research data. All study data will be maintained in password-protected, secured computer files or in locked cabinets within locked offices.

